## 6. Investigational Product

### 6.1. Formulation

All investigational products will be manufactured in accordance with Good Manufacturing Practice (GMP). Mepolizumab and placebo will be supplied by GSK in 1ml pre-filled syringes (Table 2). Mepolizumab 100mg or a normal (0.9%) saline placebo subcutaneous injection will be administered at the study centre on days 0, 28, 56 and 84 during the 12 week treatment period. The placebo will have an appearance identical to that of the study drug. Those administering treatment, any study staff involved in subject evaluations, and the subjects will remain blind to treatment assignment for the duration of the study.

**Table 2.** Intervention, dose, form, strength, and manufacturer per intervention.

Intervention	Dose	Form	Strength	Manufacturer
Mepolizumab	100mg	pre-filled (1ml) solution in syringe	100 mg/ml	GSK
Placebo - 0.9% normal saline	N/A	pre-filled (1ml) solution in syringe	N/A	GSK

### 6.2. Dosage Regimen

Patients will be randomized in 1:1 to receive mepolizumab 100mg monthly (4 doses) or matched placebo (4 doses) over 12 weeks.

### 6.3. Administration

The investigational product will be administered by an authorized study physician at McMaster University on study visits and within visit windows as described in study visits summary in section 5.6.1. Prior to administration urine pregnancy test will be done in women of childbearing potential to confirm the test is negative; the investigational product will only be administered when the result of the test is negative. The investigational product will be removed from the study refrigerator and sit at room temperature 30 minutes prior to administration.

Injections sites will be rotated such that the subjects receive the investigational product at different anatomical sites (Figure 2). The injection will be recorded in the source document at each treatment visit. After investigational product administration the subjects will be observed for a minimum of 1 hour for the appearance of any acute drug reactions. Appropriate medications such as epinephrine, antihistamines, and medical equipment to treat acute anaphylaxis must be available. Study personnel must be trained to recognise and treat anaphylaxis.

**Figure 2.** Injection sites for investigational product administration.

#### **6.4. Labelling**

Labelling will be performed according to local regulations in Canada by pharmacist or another authorised person not involved in the project. Labels will include:

- Study code
- Investigational product/study drug dosage form, route of administration, and quantity of dosage units
- Kit ID
- Lot ID
- Expiry date
- Investigator name (to be written on the label)
- Sponsor name

- Directions for use
- Storage conditions
- Standard statements required by Regulatory Authorities
- Sponsor name and contact details

## **6.5. Storage**

Mepolizumab/placebo will be stored at McMaster University, Cardio-Respiratory Research Facility, in a secure facility with limited access and controlled temperature. The temperature will be monitored on a daily basis and documented in a temperature monitoring log.

The investigational product must be kept in the original outer container and under conditions specified on the label between 2–8°C (36–46°F) and protected from the light. The recommended storage condition and expiry dates will be provided on the product labels.

## **6.6. Accountability**

The study drug provided for this study will be used only as directed in the study protocol. The study personnel will account for all study drugs dispensed to the patient. The study personnel will account for all study drugs received at the centre, unused study drugs, and for appropriate destruction. Certificates of delivery, destruction, and/or return should be signed.

## **6.7. Concomitant Medications**

Patients will be allowed to have the COVID-19 vaccination before or during the whole study duration. Any adverse effects related to vaccination will be assessed for severity by the study physician.

Patients with long standing asthma on stable doses of ICS or a combination ICS/long-acting-beta agonists (LABA) will be allowed to continue using these medications so long as the dose does not change during the study. Patients with asthma who experienced an asthma exacerbation during the treatment period will be allowed oral prednisone, with or without antibiotics, as is the current standard of care. Patients with non-asthmatic eosinophilic bronchitis who have tried ICS or a leukotriene receptor antagonist (LTRA) but for whom cough has not

improved will not be allowed to continue using ICS and LTRA and will require a washout period of 28 days prior to screening. Patients with non-asthmatic eosinophilic bronchitis with partial relief on ICS will be allowed to continue using these medications so long as the dose does not change during the study. Patients on a long-acting muscarinic antagonist (LAMA) will be required to undergo a washout period for 28 days prior to screening. Patients using SABA or LABA (in an ICS combination inhaler) will be required to withhold from using the inhaler 8 and 48 hrs prior to any methacholine challenges tests as per local SOP.

Medications not allowed are as followed: opioids (including codeine, tramadol, morphine), neuromodulators (including pregabalin, gabapentin, amitriptyline), ACE inhibitors, immunosuppressive medication (including but not limited to: methotrexate, cyclosporine, azathioprine, intramuscular long-acting depot corticosteroid, oral corticosteroid, or any experimental anti-inflammatory therapy) within 3 months of date of informed consent, and other biologics within 4 months or 5 half-lives prior to date of randomization. If the subject has been on an opioid or an opioid like medication for a long period of time for a longstanding medical condition other than chronic cough, such as but not restricted to chronic pain, neuropathic pain or fibromyalgia, then they will be allowed to continue on their usual dosage.

## **7. Assessment of Efficacy**

### **7.1. Primary Outcome**

In patients with refractory chronic cough with airway eosinophilia to measure the change in objective 24-hour cough frequency (coughs/hour) from baseline after 14 weeks of treatment with mepolizumab compared with placebo.

### **7.2. Secondary Outcomes**

In patients with refractory chronic cough with airway eosinophilia to measure changes from baseline after 8 and 14 weeks of treatment with mepolizumab compared with placebo of:

1. Awake cough frequency (coughs/hr)
2. Night-time cough frequency (coughs/hr)
3. Percentage of participants with a reduction in 24-hour cough frequency of  $\geq 30\%$

4. All cough outcomes by disease group (asthma and NAEB)
5. Cough severity and intensity of sensations (itch, tickle, irritation, urge to cough on a modified Borg Scale)
6. Quality of life measured using the Leicester Cough Questionnaire (LCQ)
7. Blood eosinophils
8. Sputum Eosinophilia (% cell count)

To determine changes from baseline after 14 weeks of treatment with mepolizumab compared with placebo of:

1. Methacholine PC20
2. Total, activated mature eosinophils, eosinophil progenitors in blood and sputum (Flow cytometry) and related transcriptomics.

## **8. Assessment of Safety**

### **8.1. Definitions**

#### *8.1.1. Adverse Events*

Adverse Events (AEs) are defined as an adverse change in health that occurs while a patient is taking part in a study. All AEs will be documented in the source documents and assessed for whether or not it is serious (see below) or expected. If not a serious adverse event (SAE), then the AE will be reported to McMaster University when copied into the Annual Progress Report if the AE was related to the study drug or a study procedure and if the event was unexpected.

#### *8.1.2. Serious Adverse Events*

Any adverse event, adverse reaction or unexpected adverse reaction, respectively, that:

- Results in death
- Is life threatening
- Requires admission to hospital or prolongation of hospitalisation
- Results in persistent or significant disability/incapacity

- Is a congenital anomaly or birth defect
- Is otherwise medically significant

## 8.2. Reporting Procedures for SAEs

Any SAE occurring between enrolment and end of protocol follow up should be recorded in the subject's hospital notes and recorded in the source documents and reported to the REB according to the current REB guidelines. The majority of SAEs will be expected complications associated with the underlying respiratory condition such as an exacerbation of asthma requiring hospital admission.

The study drug, mepolizumab, is an off-label indication for subjects recruited for this study. The Principal Investigator will therefore submit expedited reports, as indicated/necessary for reporting of serious adverse drug reactions, by fax, directly to Health Canada.

Adverse drug reactions that are *both serious and unexpected* are subject to expedited reporting to Health Canada. Expedited reporting is not required for serious events from clinical investigations that are considered unrelated to the study product, whether or not the event is expected.

In accordance with Health Canada requirements, an Adverse Drug Reaction Report will be filed in the cases

- where the adverse drug reaction is neither fatal nor life-threatening, within 15 days after becoming aware of the information.
- where adverse drug reactions is fatal or life-threatening, immediately where possible and, in any event, within 7 days after becoming aware of the information;
- within 8 days after having informed Health Canada of the adverse drug reactions, submit as complete as possible, a report which includes an assessment of the importance and implication of any findings

### 8.2.1. GSK Reporting Procedures

All safety reports and associated information, including the investigator's causality assessment, as presented in Table 3 that occur during the study in subjects exposed to the IP will be sent by email to GSK's Case Management Group (Americas), marked for the attention of the Case Administrator: [contact] or [contact] and to [name] : [contact] or [contact]. All safety reports will be submitted within 1 working day of the Principal Investigator becoming aware of the event.

Any SAEs reported by study subjects during the study which the investigator considers there to be a reasonable possibility of a causal association to any other known GSK product taken concurrently with the IP will be forwarded to GSK within 24 hours of the investigator becoming aware of the event, regardless of investigator/sponsor expectedness assessments.

Further detailed information about safety reports will be submitted to GSK within 24 hours of follow-up information becoming available.

Events exempt from reporting to GSK include any unblinded reports for subjects exposed only to placebo during the study.

The safety reports and information that are subject to the presented GSK reporting provisions are those that occur following the 1st dose of the IP through to 28 days or 5 terminal phase half-lives (whichever is longer) following discontinuation of the IP.

**Table 3.** GSK reporting safety events and information procedure

Safety Data	Format	Time Line
All SAEs that are unblinded during the course of the study, for which the investigator considers there to be a reasonable possibility of causal association with the GSK IP (as specified by the protocol), regardless of Investigator/designee/Sponsor expectedness assessments against GSK IP	Copies of Case Report Form pages	Within 24 hours of Sponsor first unblinding the event

All SAEs that remain blinded on the Sponsor database during the course of the study, where the investigator considers there to be a reasonable possibility of causal association with the GSK IP (as specified by the protocol), regardless of Investigator/designee/Sponsor expectedness assessments against GSK IP.	Copies of regulatory reports (e.g., CIOMS 1 or MedWatch)	Retrospectively within five working days of the Sponsor unblinding the study database
-----------------------------------------------------------------------------------------------------------------------------------------------------------------------------------------------------------------------------------------------------------------------------------------------------------------------	----------------------------------------------------------	---------------------------------------------------------------------------------------

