### **5. Study Design**

#### **5.1. Design**

This is a 9-visit randomized, double-blind, placebo controlled, parallel group study evaluating the effectiveness of 4 doses of mepolizumab for the treatment of refractory chronic cough in patients with eosinophilic airways disease (Figure 1). We plan to complete 15 subjects in each arm of the clinical trial. The duration of intervention will be 12 weeks, during which

subjects will receive 4 doses at days 0, 28, 56 and 84. The effects of mepolizumab on objective cough frequency will be tested at week 14, 2 weeks following the last dose of mepolizumab/placebo.

**Figure 1.** Study flow diagram detailing the study visits and procedures per visit per subject following enrolment.

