## 5.2. Duration of Study

The total length of a subject's participation in the trial is up to 16 weeks;

- Up to 2 weeks screening period
- 14-week intervention period

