***Visit 9: Final Visit: Assessment of Blood, Sputum and Questionnaires***

All subjects will undergo Ontario Covid-19 Assessment Tool and Information Letter prior to study visit. Subjects will return with the cough monitor 24 hours following Visit 8. If no recording was obtained during the past 24 hours due to recording device malfunction then the subject will be asked to repeat the recording within 24-48 hours of prior attempt at recording. Subjects will undergo spirometry, methacholine challenge, blood sampling and sputum induction and complete the Leicester Cough Questionnaire, the modified Borg Scale, and the Cough Severity VAS.

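### Possibly related serious events are reportable to GSK for at least 28 days after the last dose, but no planned contact follows the final visit, nominally 15 days after it

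*Combined protocol and SAP*

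**What the plan says.** Five parts of the combined protocol and SAP bear on when safety information stops being collected.

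- **Section 8.2.1 (GSK Reporting Procedures).** "The safety reports and information that are subject to the presented GSK reporting provisions are those that occur following the" first dose "through to 28 days or 5 terminal phase half-lives (whichever is longer) following discontinuation of the IP". Table 3 restricts its rows to SAEs that the investigator thinks may be causally linked to the product. The opening sentence of the same section describes the reports as concerning events arising in the course of the study.
- **Section 8.2 (Reporting Procedures for SAEs).** "Any SAE occurring between enrolment and end of protocol follow up should be recorded". No day is attached to that end point.
- **Section 8.1.1 (Adverse Events).** An adverse event is "an adverse change in health that occurs while a patient is taking part in a study".
- **Section 5.2 (Duration of Study).** "The total length of a subject's participation in the trial is up to 16 weeks", made up of screening of up to two weeks and a "14-week intervention period". No safety follow-up period is listed.
- **Section 5.1, section 5.10.2 and Table 1.** In section 5.1, "subjects will receive 4 doses at days 0, 28, 56 and 84". Visit 9 is labelled "Final Visit: Assessment of Blood, Sputum and Questionnaires" and falls on post-randomization day 99. The adverse-event row of Table 1 ends there.

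Section 5.14 describes no safety contact for a participant who withdraws early.

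**The concern.** The protocol sets a reporting duty that runs past the point where it stops recording SAEs and seeing participants. Section 8.2.1 also disagrees with itself: it speaks of events during the study, then sets a window that extends beyond the final visit.

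A possibly related SAE that starts after Visit 9 but inside the window would reach the site only if the participant or a treating clinician happened to report it. Staff would then find that section 8.2 does not clearly tell them to record it. Section 8.2 describes the use as off-label, and only about 15 people are planned to receive mepolizumab, so a single missed event would be a material part of the safety information.

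**Working it through.** **Inputs**

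- Last dose: post-randomization day 84, study day 99 ± 3 (section 5.1; Table 1, Visit 7).
- Final visit: post-randomization day 99, study day 114 ± 3 (Table 1, Visit 9).
- Reporting window: the longer of 28 days and five terminal half-lives after discontinuation (section 8.2.1).
- Half-life: not given, so treated as unknown.
- Assumption: for a completer, discontinuation is dated from the fourth dose.

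**Step 1. Reproduce the stated length of participation.** 2 + 14 = 16 weeks = 112 days. Table 1 runs from study day 1 to study day 114, which is 113 days. The two agree within one day, so Visit 9 is the end of participation as section 5.2 describes it.

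**Step 2. Nominal time observed after the last dose.** 99 − 84 = 15 days on the post-randomization row and 114 − 99 = 15 days on the study-day row. (The two rows differ by 14 days up to Visit 6 and by 15 days from Visit 7, but this does not affect the interval.)

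**Step 3. Nominal gap against the 28-day floor.** 28 − 15 = 13 days, or 13/28 = 46% of the minimum window. The floor ends on post-randomization day 84 + 28 = 112.

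**Step 4. Effect of the visit windows.**

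- Shortest: Visit 7 at +3, Visit 9 at −3: (114 − 3) − (99 + 3) = 9 days observed, 28 − 9 = 19 uncovered.
- Longest: Visit 7 at −3, Visit 9 at +3: (114 + 3) − (99 − 3) = 21 days observed, 28 − 21 = 7 uncovered.
- Visit 8 has ± 7 days. With Visit 7 at −3, Visit 8 at +7 and Visit 9 the next day: (113 + 7 + 1) − (99 − 3) = 25 days, still under 28. Study day 121 is already outside Visit 9's own limit of 114 + 3 = 117. Reaching 28 days needs a late repeat recording as well (up to 3 more days).

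So no schedule within the Visit 7 and Visit 9 windows covers the 28-day floor.

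**Step 5. Effect of the unknown half-life.** Window = max(28, 5 × half-life); nominal gap = window − 15. The half-lives below are illustrative assumptions.

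| Assumed half-life (days) | Window (days) | Nominal gap (days) |
|---|---|---|
| 5.6 or less | 28 | 13 |
| 7 | 35 | 20 |
| 14 | 70 | 55 |
| 20 | 100 | 85 |

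The mismatch exists at any half-life, because 28 days is the floor. Only its size depends on the half-life.

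**The case against.** The strongest reply is that section 8.2.1 is a rule for forwarding reports to the drug supplier. Its clock starts when the investigator becomes aware of an event, and Table 3 limits it to possibly related SAEs. A passive duty of that kind can run longer than the visit schedule without contradiction, and the protocol nowhere promises contact to day 112. This stands as a limit on the point: a reader might infer that the trial undertakes active surveillance of all adverse events for 28 days, and the documents do not say so. It does not remove the point, since section 8.2 gives no clear instruction to record a late event and nothing in the schedule elicits one.

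Second, the end of follow-up in section 8.2 has no stated day, so the 15 days is inferred from Visit 9 and the 16-week limit. That is correct. If a later date is meant, it is unwritten and needs to be added.

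Third, late events could surface through clinical care, and the Health Canada duty in section 8.2 has no stated end date. Section 8.3 also reports that injection-site reactions came mainly early in treatment and that most systemic reactions occurred on the day of dosing. With about 30 participants, few events would be expected in the uncovered days. This limits the likely yield. It does not supply a planned means of capture.

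**Conclusion.** Followed as written, the protocol has no planned means of learning of possibly related SAEs in the last part of its own reporting window. The gap is nominally 13 of the minimum 28 days, and 7 to 19 days within the Visit 7 and Visit 9 windows. It is longer if five half-lives exceed 28 days. This rests on Visit 9 being the end of follow-up and on discontinuation being dated from the last dose. Participants who stop early may have a larger gap, because no later contact is described for them.

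Three stronger readings are not supported:

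- That every completer has at least 13 uncovered days. Thirteen is the nominal value, and the visit windows allow as few as 7.
- That the trial's safety summary would claim follow-up that was not done. Section 9 specifies no safety analysis and describes no such summary.
- That the loss would favour one arm. Allocation is masked, and the documents give no mechanism for a difference.

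The number of events that would be missed cannot be estimated from the documents. The primary endpoint is unaffected. This is a cheap improvement to safety capture.

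**What to change.** Reconcile sections 5.2, 8.1.1, 8.2, 8.2.1 and Table 1 so that SAE recording and SAE reporting share one dated end, expressed in days after the last dose, and state the half-life used to set it. How long that period should be is for the sponsor to settle with the supplier.

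If the section 8.2.1 window is kept:

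- Extend SAE recording in section 8.2 to the end of that window, and align the wording of section 8.1.1 and the opening of section 8.2.1.
- Add to Table 1 one closing telephone contact by existing staff, with no procedures, at or after the end of the window. On the 28-day floor this is no earlier than post-randomization day 112 for a participant dosed on day 84, and later if five half-lives is the longer limb.
- Include participants who stop early and agree to be contacted, timed from their own last dose.
- Update section 5.2. On the 28-day floor the total becomes 2 + 12 + 4 = 18 weeks, against the present 16.

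The cost is about 30 short calls (15 per arm × 2 arms, one each) and revised protocol and consent wording. The efficacy analysis and the dosing schedule do not change.

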### 8.3. Adverse Events with Mepolizumab

*Local injection site reactions:* In 2 placebo-controlled studies the incidence of local injection site reactions with mepolizumab 100 mg subcutaneous and placebo was 8% and 3%, respectively. These events were all non-serious, mild to moderate in intensity and the majority resolved within a few days. Local injection site reactions occurred mainly at the start of treatment and within the first 3 injections with fewer reports on subsequent injections. The most common manifestations reported with these events included pain, erythema, swelling, itching, and burning sensation.

*Serious adverse events:* One SAE occurred in >1 patient and more frequently with mepolizumab than placebo: herpes zoster (2 vs 0 patients).

*Systemic reactions:* In the 3 clinical trials, the percentages of subjects who experienced systemic (allergic and nonallergic) reactions were 3% for mepolizumab and 5% for placebo. Manifestations included rash, flushing, pruritus, headache, and myalgia. A majority of the systemic reactions were experienced on the day of dosing.

**Table 4.** A pooled summary of adverse events in the first 24 weeks of 2 trials (MENSA and SIRIUS).

Adverse Event	Mepolizumab (n=263)	Placebo (n=257)
Headache	19%	18%
Injection site reaction	8%	3%

Back pain	5%	4%
Fatigue	5%	4%
Influenza	3%	2%
Urinary tract infection	3%	2%
Abdominal pain upper	3%	2%
Pruritus	3%	2%
Eczema	3%	<1%
Muscle spasms	3%	<1%

